9.2 Primary Efficacy Criteria

The change in maximum keratometry (Kmax) from baseline will be evaluated at 12 months. Data will be summarized using descriptive statistics, and a one-group t-test comparing the mean change from baseline value to the target value of 0.75 D will be performed.

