1.2 Prior Experience

United States Phase 3 Clinical Studies

The safety and efficacy of the corneal collagen cross-linking procedure were evaluated in 3 randomized, parallel-group, open-label, sham-controlled trials; patients were followed

² Pinelli R, Mometto C. Corneal epithelium: Should it stay or should it go? Ophthalmology times Europe, April 2007, pages 18-19. Available at <http://www.oteurope.com/ophthalmologytimeseuropa/Cornea/Corneal-epithelium-should-it-stay-or-should-it-go/ArticleStandard/Article/detail/415196>

³ Chan CCK, Sharma M, Boxer Wachler BS. Effect of inferior-segment Intacs with and without Cx-R on keratoconus. J Cataract Refract Surg. 2007;33:75-80.

for up to 12 months. In each study, only one eye of each patient was designated as the study eye. Study eyes were randomized to receive one of the two study treatments (CXL or sham) at the baseline visit and were followed up at Day 1, Week 1, and Months 1, 3, 6, and 12. At Month 3 or later, sham study eyes and non-study eyes had the option of receiving CXL treatment, and were followed-up for 12 months from the time of receiving CXL treatment. Each CXL treated eye received a single course of CXL treatment only. Overall, 512 eyes (293 keratoconus, 219 corneal ectasia) in 364 patients received CXL treatment.

In each study, the maximum corneal curvature (Kmax) was assessed at baseline, Months 1, 3, and 12. The CXL-treated eyes showed increasing improvement in Kmax from Month 3 through Month 12. Progressive keratoconus patients had an average Kmax reduction of 1.4 diopters in Study 1 and 1.7 diopters in Study 2 at Month 12 in the CXL treated eyes while the sham eyes had an average increase of 0.5 diopter in Study 1 and 0.6 diopter in Study 2 at Month 12; the difference (95% CI) between the CXL and sham groups in the mean change from baseline Kmax were -1.9 (-3.4, -0.3) diopters in Study 1 and -2.3 (-3.5, -1.0) diopters in Study 2.

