The most common ocular adverse reactions in any CXL-treated eye were corneal opacity (haze), punctate keratitis, corneal striae, corneal epithelium defect, eye pain, reduced visual acuity, and blurred vision. These events are expected sequelae following epithelial corneal debridement and occurred at a higher incidence than observed in control patients, who did not undergo debridement or exposure to UVA light. The majority of adverse events reported resolved during the first month, while events such as corneal epithelium defect, corneal striae, punctate keratitis, photophobia, dry eye and eye pain, and decreased visual acuity took up to 6 months to resolve and corneal opacity or haze took up to 12 months to resolve. In 1-2% of patients, corneal epithelium defect, corneal edema, corneal opacity and corneal scar continued to be observed at 12 months.

Epithelium-on Corneal Collagen Crosslinking

Modifications to the standard CXL technique have been undertaken by a number of investigators with varying results. Addition of preoperative anesthetic drops containing BAK serves to loosen the epithelial cell tight junctions and appears to result in crosslinking without the delayed wound epithelial healing effects and immediate postoperative period discomfort.⁸

A prospective clinical trial evaluating an approach comparable to the method proposed in this study has been conducted in the United States. Epithelium-on CXL was performed in eyes with keratoconus using proparacaine with BAK 0.01% to facilitate riboflavin absorption and riboflavin 0.10% without dextran. Eyes were randomized to receive ultraviolet-A treatment (365 nm, 3 mW/cm²) with concurrent administration of riboflavin randomized to every 1 minute or every 2 minutes for 30 minutes. Patients were followed for 6 months. Thirty eyes of 25 patients were treated. The mean maximum K value flattened by 0.9 diopter (D) (baseline 58.7 D; 6 months 57.8 D). The maximum K worsened by 2.0 D or more in 1 patient. The mean CDVA improved by 0.83 Snellen

lines. One patient lost 2 lines of CDVA. There were no differences in the UDVA, CDVA, or keratometry outcomes between the 1-minute instillation subgroup and the 2-minute instillation subgroup.⁴

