9.0 DATA ANALYSIS AND STATISTICAL CONSIDERATIONS

Tabulation of summary statistics, graphical presentations, and statistical analyses will be performed. All subjects who are enrolled and treated in this study will be included in the safety analysis. All two sided testing and confidence intervals will use a significance level of 5%.

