9.1 Sample Size

The primary efficacy analysis for the treatment of keratoconus is to determine whether the mean decrease in Kmax from baseline to 12 months is at least 0.75 D.

Based on paired T statistics, assuming a population standard deviation of 2.5 D, a two-sided threshold probability of rejecting the null hypothesis (alpha) of 0.05, and 80% power to detect a difference from baseline of 0.75D, a sample size of 89 evaluable eyes is needed.

The primary efficacy analysis will follow an intent-to-treat (ITT). The ITT population consists of any study eye enrolled in the study (defined as having the study drug instilled). The ITT population will be used for all safety and efficacy evaluations.

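### The 80% power in Protocol 9.1 is for a test against zero change, but the primary test in 9.2 is against 0.75 D

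*Protocol*

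**What the plan says.** Protocol 9.1 (Sample Size) opens by giving the aim of the primary efficacy analysis: to determine "whether the mean decrease in Kmax from baseline to 12 months is at least 0.75 D". The calculation that follows uses a paired t statistic, an SD of 2.5 D and a two-sided test at the 5% level. Its stated result is: "80% power to detect a difference from baseline of 0.75D, a sample size of 89 evaluable eyes is needed".

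Protocol 9.2 (Primary Efficacy Criteria) specifies the test at 12 months: "a one-group t-test comparing the mean change from baseline value to the target value of 0.75 D will be performed".

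Protocol 1.2 (Prior Experience) gives the only effect sizes in the document. In the epithelium-off phase 3 studies, treated keratoconus eyes had an "average Kmax reduction of 1.4 diopters in Study 1 and 1.7 diopters in Study 2 at Month 12". In the cited epithelium-on study (30 eyes, 6 months, riboflavin 0.10%) the mean flattening was 0.9 D.

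**The concern.** The same 0.75 D has two roles that cannot both hold for one test. In the power statement it is a difference from baseline, so the null is zero change and 0.75 D is the alternative. In 9.2 it is the value against which the mean change is compared, so it is the null. The aim at the start of 9.1 agrees with 9.2; the power statement is the one that does not fit.

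Two things are at stake. First, the quoted 80% describes a test that is not planned, and the power of the planned test depends on a true decrease that the protocol never states, so nobody can judge whether 89 eyes are enough. Second, the criterion for success is open to two readings. With 89 eyes and an SD of 2.5 D, an observed mean decrease of 0.9 D would be clearly significant against zero and far from significant against 0.75 D. In a study without a control arm, that choice should not be left until the data are seen.

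**Working it through.** **Inputs.** Protocol 9.1: n = 89 evaluable eyes, SD of change 2.5 D, two-sided alpha 0.05, 80% power, difference 0.75 D. Protocol 9.2: null value 0.75 D. Protocol 1.2: reported mean decreases of 0.9, 1.4 and 1.7 D. Eyes are treated as independent throughout.

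**Step 1: reproduce the protocol's figure (null = 0).** The standardised difference is 0.75/2.5 = 0.30.

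- Normal approximation: n = [2.5 × (1.960 + 0.842)/0.75]² = 87.2, so 88.
- Exact t: noncentrality 0.30 × √89 = 2.83, df 88, critical value 1.987, power 79.9%. With 90 eyes it is 80.4%.
- A one-sided 0.05 test would need only 71 eyes, so it is not the source of 89.

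The 89 eyes therefore come from a two-sided test against zero change.

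**Step 2: the 9.2 test with the same n, SD and alpha (null = 0.75 D).** The standard error is 2.5/√89 = 0.265 D and the half-width of the 95% CI is 1.987 × 0.265 = 0.527 D. To be significantly above the target, the observed mean decrease must exceed 0.75 + 0.527 = 1.277 D. Against zero the threshold is 0.527 D.

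Power to show a decrease greater than 0.75 D comes from the noncentral t with noncentrality (true decrease − 0.75)/0.265:

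| True mean decrease | Noncentrality | Power, 89 eyes | Eyes for 80% |
|---|---|---|---|
| 0.75 D (the null itself) | 0 | 2.5% | – |
| 0.9 D (epithelium-on, 6 months) | 0.57 | 8.1% | 2183 |
| 1.0 D (illustrative) | 0.94 | 15.2% | 787 |
| 1.4 D (epithelium-off, Study 1) | 2.45 | 67.9% | 119 |
| 1.5 D (0.75 D beyond target) | 2.83 | 79.9% | 90 |
| 1.7 D (epithelium-off, Study 2) | 3.58 | 94.4% | 57 |

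The 1.5 D row has the same noncentrality as Step 1. The stated power is recovered only if the true decrease is twice the value named in 9.1.

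**Step 3: the two readings on one result.** For an observed mean decrease of 0.9 D with SD 2.5 D, t = 0.9/0.265 = 3.40 against zero and t = (0.9 − 0.75)/0.265 = 0.57 against 0.75 D. The critical value is 1.987.

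**The case against.** The strongest reply is that 9.2 is a valid and stricter test. It does not inflate the type I error, and a true decrease near 1.5 D is not fanciful given 12-month reductions of 1.4 and 1.7 D in the phase 3 studies. On that view only the power statement needs correcting. Three further points limit the alarming end of the range:

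- The 2.5% at a true 0.75 D is the rejection rate at the null in one direction. Any test has it, whatever its size, so it says nothing about whether 89 eyes suffice.
- The 0.9 D result is from 6 months. Protocol 1.2 reports that Kmax kept improving to month 12 after epithelium-off treatment. If that carries over, which is an assumption, 8% is pessimistic.
- If all of the roughly 100 enrolled eyes contributed, power would be 73% at 1.4 D and 84% at 1.5 D.

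These points hold, and the range to read is 8% to 94%, not 2.5% to 94%. They do not remove the mismatch. The protocol states no decrease above 0.75 D, and the 1.4 and 1.7 D results come from a different procedure. Nor is this a detail left to an analysis plan: the protocol itself fixes both the basis of the sample size and the test, so a plan that follows one departs from the other. A one-sided reading does not help, since at a true decrease equal to the null value the rejection rate is alpha.

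**Conclusion.** The concern holds. The sample-size arithmetic is right for a test against zero. The fault is that the hypothesis powered in 9.1 is not the one tested in 9.2, so the stated 80% does not apply to the primary test. For that test, 89 eyes give 80% power only at a true decrease of about 1.5 D; at the decreases cited in Protocol 1.2, power is 8%, 68% or 94%.

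The figures assume the protocol's SD of 2.5 D. At a true decrease of 1.4 D, power would be 86% with an SD of 2.0 D and 52% with 3.0 D (illustrative values). They also assume independent eyes. Protocol 8.3 allows both eyes of a subject to take part, and positive correlation between fellow eyes would lower power under either reading. Because this is the only primary efficacy test and its success criterion is ambiguous, it should be settled before analysis.

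**What to change.** The sponsor should choose one null value and make 9.1 and 9.2 agree. Section 9.2 gives no sign for the change, so either option should define the decrease as baseline minus month 12. If change is instead taken as month 12 minus baseline, the target becomes −0.75 D.

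**(a) Test against zero.** In 9.2: H0, mean decrease in Kmax = 0, two-sided 0.05; success if the 95% CI lies wholly above 0; the estimate and CI are reported beside 0.75 D as a reference value. Reword the aim in 9.1 to whether mean Kmax decreases, with 0.75 D as the planning difference. The 89 eyes and about 80% power stand, assuming independent eyes. The cost is a weaker claim: that Kmax is reduced, not that it is reduced by at least 0.75 D. That is a lower bar in a study without a control arm, and it departs from the aim as now stated.

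**(b) Keep 0.75 D as a performance goal.** In 9.2: H0, mean decrease ≤ 0.75 D; success if the lower limit of the two-sided 95% CI exceeds 0.75 D. In 9.1: state that 89 eyes give about 80% power if the true mean decrease is about 1.5 D with SD 2.5 D, and justify that decrease. This keeps the stated aim and test. It needs no extra eyes only if about 1.5 D can be defended. Otherwise the stated power must fall (68% at 1.4 D) or the number of evaluable eyes must rise (119 at 1.4 D).

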6.0 SUBJECT POPULATION

Approximately 100 eyes will be enrolled to provide at least 89 evaluable eyes at 12 Months post-procedure.

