8.3 Follow-Up Visits (1 Day, 1 Week, 1, 3, 6, and 12 Months)

All subjects will be seen at 1 day, 1 week, 1, 3, 6, 12 months after CXL. The week 1 visit should be between 5 and 9 days. The one month visit should be between 1 week before and 1 week after the one month date. The three month visit should be between 2 weeks before and 2 weeks after the three month visit. The six month visit should be between 2 weeks before and 2 weeks after the six month visit. The twelve month visit should be between 1 month before and 1 month after the twelfth month visit. If a subject has both eyes involved in the study, and coordinating office visits becomes a burden to the patient due to the two eyes not being in synch, it will be up to the investigator's discretion to allow study visits outside of the above schedule.

The following will be performed at each visit unless noted otherwise:

- UCVA distance
- Slit lamp examination of the cornea, anterior chamber and lens
- Documentation of interim medical, medication, and ocular histories.

The following tests will be additionally performed at the 1, 3, 6 and 12 Month visits:

- BSCVA distance
- Pentacam measurements

Reasonable effort will be made by telephone and mail to contact subjects who miss a scheduled follow-up visit.

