9.6 Dropouts/Lost-to-Follow-up

Patients may drop out at any time during the study. All treated patients/eyes will be included in the safety analysis.

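### Sections 9.1 and 9.2 do not reconcile an ITT primary analysis of every instilled eye with a 12-month one-group t-test sized on 89 evaluable eyes

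*Protocol*

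**What the plan says.** **The set.** Protocol section 9.1 applies ITT to the primary efficacy analysis and defines it: "The ITT population consists of any study eye enrolled in the study (defined as having the study drug instilled". It adds: "The ITT population will be used for all safety and efficacy evaluations".

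**The method.** Section 9.2: "The change in maximum keratometry (Kmax) from baseline will be evaluated at 12 months". The test follows: "a one-group t-test comparing the mean change from baseline value to the target value of 0.75 D will be performed".

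**The size.** Section 6.0: "Approximately 100 eyes will be enrolled to provide at least 89 evaluable eyes at 12 Months post-procedure". Section 9.1 computes the same 89 evaluable eyes from a paired t statistic.

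**Eyes that leave.** Section 9.6 speaks of one analysis only: "All treated patients/eyes will be included in the safety analysis". Section 8.5 asks for a final examination at withdrawal where possible, but does not name Pentacam or link that examination to the primary test.

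**Data available.** Section 8.3: "The following tests will be additionally performed at the 1, 3, 6 and 12 Month visits". Pentacam is on that list, so an eye lost late in the year will usually have earlier Kmax values. Section 4.0 also describes the primary parameter as Kmax change over time.

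**The concern.** The protocol names one set (all instilled eyes), sizes on another (evaluable eyes), and chooses a test that needs a Month 12 value from each eye. An eye without that value can enter only through a step that the protocol does not state. If no such step is added, a completers' result would carry an ITT label, and the Kmax readings at Months 1, 3 and 6 from the lost eyes would go unused.

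This matters more than it would in a randomised comparison. Every eye is treated and the mean is compared with a fixed value, so no control arm can offset attrition. If eyes that steepen are more likely to leave, the estimated flattening moves directly in the favourable direction. A completers' mean is in general unbiased for all instilled eyes only if leaving is unrelated to the 12-month change.

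The repeated-measures analysis in section 9.3 does not fill the gap. It follows the acuity outcomes and lists Months 1, 3 and 6.

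**Working it through.** **1. The plan's own figure.** Inputs from section 9.1: SD 2.5 D, difference 0.75 D, two-sided alpha 0.05, power 80%.

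- Normal formula: n = (2.5 × (1.960 + 0.842) / 0.75)² = 87.2, so 88 eyes.
- Exact noncentral t: 79.9% power at 89 eyes, 80.4% at 90.

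The stated 89 is reproduced within rounding.

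**2. Implied loss.** 89 / 100 leaves 11%, and 89 / (1 − 0.11) = 100. The protocol states no dropout rate; the 11% is what its two counts imply as an upper allowance.

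**3. Bias of a completers' mean.** Bias = missing share × (mean in observed eyes − mean in missing eyes). With a share of 0.11:

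- missing eyes worse by 0.5 D: 0.11 × 0.5 = 0.06 D
- worse by 1.25 D: 0.11 × 1.25 = 0.14 D
- worse by 2.75 D: 0.11 × 2.75 = 0.30 D

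**4. Linking the bias to dropout strength.** Assumptions, none from the protocol: the chance of missing Month 12 is logistic in standardised Month 6 steepening, with an odds ratio (OR) per SD of 1.25 to 4.5, calibrated to 11% missing; the correlation r between the Month 6 and Month 12 changes is 0.5 to 0.8. Let m be the mean standardised Month 6 change in retained eyes, counted in the direction of flattening. Then bias = r × 2.5 × m.

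| OR per SD | m | bias, r = 0.5 | bias, r = 0.8 |
|---|---|---|---|
| 1.25 | 0.0244 | 0.03 D | 0.05 D |
| 1.5 | 0.0439 | 0.05 D | 0.09 D |
| 2.0 | 0.0726 | 0.09 D | 0.15 D |
| 4.5 | 0.1328 | 0.17 D | 0.27 D |

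**5. What these biases imply for the lost eyes.** If the all-eyes mean is −0.75 D, the missing eyes average −0.75 + (0.89 / 0.11) × bias:

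- bias 0.03 D: about −0.5 D
- bias 0.09 D: about 0 D
- bias 0.27 D: about +1.4 D

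For comparison, section 1.2 reports that sham eyes steepened by 0.5 and 0.6 D at Month 12.

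**6. Effect on the test.** SE = 2.5 / √89 = 0.265 D. When the true all-eyes mean lies exactly on the reference value, the chance of a favourable rejection is P(Z > 1.96 − bias / 0.265), instead of 2.5%:

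- bias 0.03 D: 3.2%
- bias 0.09 D: 5.3%
- bias 0.14 D: 7.6%
- bias 0.27 D: about 17%

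These rates are the same whichever reference value is tested.

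**7. A mild case.** Set 11 missing eyes to no change while the observed eyes average a 0.75 D decrease. The all-eyes mean decrease is 0.89 × 0.75 = 0.67 D, the SD is √(0.89 × 6.25 + 0.89 × 0.11 × 0.5625) = 2.37 D, and power against zero with n = 100 is 79.6%, close to the planned 80%.

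**The case against.** A reader might infer that section 9.2 prescribes a complete-case analysis and so flatly contradicts section 9.1. The text does not go that far. Section 9.2 gives an endpoint, a time point and a test; it does not say which eyes enter. A one-group t-test can be run on an ITT set with imputed values, and the withdrawal examination in section 8.5 might supply a last value for some eyes. Missing-data rules are commonly left to the SAP, which is not at hand, so the silence of section 9.6 on efficacy is not an error in itself. All of this stands. What remains is that the protocol commits to a set, a sample size basis and a method that fit together only through an unstated step.

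A reader might also infer that the primary result will be biased. The protocol gives no information on why eyes would leave, so the dropout strength and correlations above are assumptions. The upper end is demanding: lost treated eyes would have to steepen by about 1.4 D, more than twice the change in sham eyes. The low-end biases are a third of a standard error or less.

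Finally, the merit of a mixed model should not be oversold. In simulation, an estimate using Months 1, 3 and 6 came within 0.01 D of the truth, but only because dropout was made to depend on observed values and every lost eye had those three visits. Loss before Month 6, or loss driven by unseen later steepening, was not covered. A model that needs one post-baseline scan also leaves out some instilled eyes, so it has to be paired with a sensitivity analysis that includes them.

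**Conclusion.** The point holds as a failure to reconcile. Section 9.1 promises every instilled eye; sections 6.0 and 9.1 size on 89 of about 100; and the section 9.2 test, run without imputation, would use only eyes with a Month 12 Kmax.

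The consequence is a risk of overstated flattening: about 0.03 to 0.09 D if leaving depends weakly on steepening (OR 1.25 to 1.5 per SD) and 0.09 to 0.27 D if strongly (2.0 to 4.5). Only the SD of 2.5 D and the implied 11% loss come from the protocol. Relative to the 0.265 D standard error this ranges from minor to about one standard error. It is worth correcting because the trial has no control arm and the data needed for a better estimate are already being collected. It does not show that the planned result would be wrong.

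**What to change.** **Section 9.2, primary analysis.** Estimate and test the Month 12 mean change from a repeated-measures mixed model on Kmax change at Months 1, 3, 6 and 12. Include visit, centred baseline Kmax and an unstructured covariance across visits, with subject-level clustering where both eyes are enrolled (section 8.3 allows this). Use all instilled eyes with at least one post-baseline Pentacam.

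**Section 9.2, sensitivity analyses.**

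- Keep the one-group t-test on completers.
- Add an analysis in which all instilled eyes without Month 12 data, including those with no post-baseline scan, are shifted in the unfavourable direction. This covers the full set in section 9.1 and tests the missing-at-random assumption.

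**Section 9.1.** State that the 89 evaluable eyes are those expected to have a Month 12 Kmax, and that the ITT set is larger.

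**Cost.** Wording only: no new visits, eyes or measurements. The small downside is that a model assuming data are missing at random replaces a simple t-test.

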9.3 Additional Analyses

Change in BSCVA and UCVA compared to the baseline examination will be evaluated at 12 months postoperatively. Data will be summarized using descriptive statistics. As a secondary analysis of this endpoint, a repeated measures analysis of variance will be conducted to assess the profile of the treatment across time at 1 month and again at 3, and 6 months following the CXL procedure.

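### The repeated-measures ANOVA named in 9.3 for BSCVA and UCVA, in its classical form, drops any eye that misses a listed visit; a mixed model would fit the ITT rule in 9.1 better

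*Protocol*

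**What the plan says.** Protocol 9.3 covers change in BSCVA and UCVA. The 12-month change is summarised descriptively. Then, "As a secondary analysis of this endpoint", the protocol states that "a repeated measures analysis of variance will be conducted to assess the profile of the treatment across time", with the visits given as "across time at 1 month and again at 3, and 6 months following the CXL procedure". It gives no fitting method, covariance structure or rule for an eye with a missed visit.

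Protocol 4.0 classes uncorrected and best corrected acuity as efficacy, so the population rule in 9.1 governs this analysis: "The ITT population will be used for all safety and efficacy evaluations". Membership in 9.1 depends only on the study drug having been instilled, not on later attendance.

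Three places expect incomplete follow-up:
- 6.0: "Approximately 100 eyes will be enrolled to provide at least 89 evaluable eyes at 12 Months post-procedure".
- 8.3 provides for contacting subjects who miss a visit. It also lets the investigator allow visits outside the schedule when both eyes of a subject are in the study.
- 9.6: "Patients may drop out at any time during the study". That section then deals only with the safety analysis.

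**The concern.** Classical repeated-measures ANOVA needs a complete row for each eye. An eye seen at months 1 and 6 but not at month 3 is removed altogether, including its two observed acuity values. The ITT rule would keep that eye. The univariate F-test also assumes sphericity, meaning equal variances of all between-visit differences. That is doubtful for visits spaced 1, 3 and 6 months after a procedure, during recovery, and the test is anti-conservative when the assumption fails.

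At stake is the only model the protocol names for acuity over time. Protocol 1.1 lists faster visual recovery among the potential benefits of leaving the epithelium on, so this profile is likely to be read with interest. If eyes that miss visits are doing better or worse than the others, the profile is biased. If they are not, precision is still lost.

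**Working it through.** **The plan's own figure.** The protocol gives no number for this analysis. Its only sample-size figure is the 89 evaluable eyes for the primary Kmax analysis (9.1: SD 2.5 D, difference 0.75 D, two-sided alpha 0.05, power 80%).
- Normal approximation: n = (2.5 × (1.960 + 0.842) / 0.75)² = 87.2, rounded up to 88.
- Exact t calculation: power 79.9% at n = 89 and 80.4% at n = 90.

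The stated 89 is reproduced within rounding. The enrolment allowance is 100 − 89 = 11 eyes, and it applies at month 12.

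**Eyes lost from a complete-case ANOVA at months 1, 3 and 6.** Let d be the proportion that has dropped out by month 6, and m the proportion missing each visit independently. The protocol gives neither, so both are assumptions.

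Eyes kept per 100 = 100 × (1 − d) × (1 − m)³

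- Monotone dropout only (m = 0): d = 11% keeps 89 and loses 11; d = 5.5% keeps 94.5. The 11% case takes all the month-12 allowance as lost by month 6, so it is the maximum within that allowance.
- Independent misses only (d = 0): m = 3% keeps 100 × 0.97³ = 91.3 and loses about 9; m = 5% keeps 100 × 0.95³ = 85.7 and loses about 14.
- Both together: d = 5.5%, m = 5% keeps 81.0; d = 11%, m = 5% keeps 76.3.
- Neither: all 100 are kept and the concern has no effect.

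**Precision.** Treating eyes as independent, the standard error of a visit mean grows by the square root of 100 / eyes kept: √(100/91.3) = 1.05, √(100/89) = 1.06, √(100/85.7) = 1.08. That is 5 to 8% relative to complete data on all eyes. A model using all available values recovers part of it.

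**Bias.** A simulation had eyes leave after a poor month-1 result, with 11% lost and an assumed between-visit correlation of 0.5 to 0.7. Complete eyes then overstated the mean change as follows:
- Moderate dependence (odds ratio 2.7 per SD): about 0.10 SD at month 1, and 0.05 to 0.07 SD at months 3 and 6.
- Exactly the worst 11% leave: 0.21 SD at month 1, and 0.10 to 0.15 SD at months 3 and 6.
- Loss unrelated to outcome: zero.

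In this mechanism the loss depends on an observed value, so it is missing at random. A correctly specified likelihood-based model handles that case and a complete-case analysis does not.

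**The case against.** The strongest reply is that the protocol names a family of methods and stops there. The term repeated-measures ANOVA is also used for likelihood-based fits that keep incomplete eyes. Fitting method, covariance structure and sphericity correction commonly belong in the SAP, which is not shown. This stands in part. A reader might infer from 9.3 that incomplete eyes will be excluded, but no section says so, and the point holds only for the classical form. It is still more than missing detail: the protocol commits to a named method whose classical meaning fits poorly with a rule stated in 9.1.

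A second reply is that ITT defines which eyes belong, not that each has data at every visit; 6.0 itself separates enrolled from evaluable eyes. That is fair, and no model can use an eye with no post-baseline acuity. What the ITT rule does not accommodate is discarding values that were observed.

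Third, the size is assumed. A reader might take the 11% allowance as a miss rate at each of the three visits and conclude that about 30 of 100 eyes are lost (1 − 0.89³ = 0.295). The documents do not support that: 11% is a cumulative allowance at month 12, a visit outside the listed three. A reader might also infer that the profile is biased, but nothing in the documents shows that missed visits relate to outcome.

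Finally, no figure in the protocol shows that sphericity fails, and degrees-of-freedom corrections exist. Those corrections do not bring back the dropped eyes.

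**Conclusion.** The point holds as a low-severity improvement to a stated method. In its classical form the ANOVA in 9.3 uses only eyes seen at months 1, 3 and 6. That fits poorly with the ITT rule in 9.1 and with the incomplete follow-up that the protocol expects.

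The loss is at most about 11 of 100 eyes under monotone dropout within the 6.0 allowance, and about 9 to 14 under independent misses at an assumed 3 to 5% per visit. It would be larger if both occur and zero if neither does. Bias requires missingness related to outcome; otherwise the cost is precision alone.

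The primary Kmax t-test, the 89-eye calculation and the descriptive 12-month acuity summary do not depend on this analysis.

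**What to change.** In 9.3, replace the repeated-measures ANOVA with a likelihood-based linear mixed model for change from baseline in BSCVA and, separately, UCVA:
- visit as a category: the listed 1-, 3- and 6-month visits, plus month 12 if wanted. Name the visits, because 8.3 does not schedule BSCVA at day 1 or week 1;
- unstructured covariance between visits within an eye;
- a patient-level random effect, or an equivalent, because 8.3 allows both eyes of a subject in the study;
- all available data from ITT eyes with a baseline and at least one post-baseline value;
- estimated mean change with 95% CI at each visit.

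The cost is a sentence or two in 9.3, with the detail in the SAP, using standard software and no new data. The downside is reliance on missing-at-random, which is a weaker assumption than a complete-case analysis generally needs.

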4.0 SAFETY AND EFFICACY ENDPOINTS

The primary efficacy parameter is the change from baseline over time in maximum keratometry (Kmax). Additional analyses for efficacy will include uncorrected visual acuity (UCVA) and best corrected visual acuity (BCVA).

Safety assessments will include a tabulation of adverse events, loss of visual acuity >3 lines, slit lamp examination of the cornea and lens, and contact lens tolerance for contact lens wearers.

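### The repeated-measures analysis in 9.3 is presented as a secondary analysis of the 12-month acuity endpoint, but its visit list stops at month 6

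*Protocol*

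**What the plan says.** Protocol 9.3 opens with the acuity endpoint and its time: "Change in BSCVA and UCVA compared to the baseline examination will be evaluated at 12 months postoperatively". After a sentence on descriptive statistics, it introduces a repeated-measures analysis of variance, describes it as a secondary analysis of the endpoint just named, and states its purpose and visits: "to assess the profile of the treatment across time at 1 month and again at 3, and 6 months following the CXL procedure".

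Protocol 8.3 gives the measurement schedule. UCVA is in the list headed "The following will be performed at each visit unless noted otherwise". BSCVA and Pentacam are in the list headed "The following tests will be additionally performed at the 1, 3, 6 and 12 Month visits".

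Two further statements bear on how the model should be fitted. On the analysis population, 9.1 says "The ITT population will be used for all safety and efficacy evaluations", and it defines that population as every study eye in which study drug was instilled. Section 8.3 provides for bilateral participation: "If a subject has both eyes involved in the study".

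**The concern.** The endpoint is at month 12, and the model presented as a secondary analysis of it ends at month 6. A model fitted to months 1, 3 and 6 has no month-12 parameter. It can describe the early course, but it cannot estimate or test the change at the endpoint visit.

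What would be lost is the late part of the profile. If the analysis were run as written, the only model-based description of acuity over time would be silent on whether acuity held, improved or fell between month 6 and month 12. That interval is half of the planned follow-up (12 − 6 = 6 of 12 months). The data to fill it are already scheduled.

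This is not a detail left to the statistical analysis plan. The protocol names the visits, and the list conflicts with the endpoint time given in the same section.

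**Working it through.** **The plan's own figure.** The protocol gives no figure for the acuity analysis. Its only computed figure is the 89 evaluable eyes in 9.1, which rests on Kmax: SD 2.5 D, difference 0.75 D, two-sided alpha 0.05, power 80%.

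- Normal approximation: n = ((1.960 + 0.842) × 2.5 / 0.75)² = 87.2, rounded up to 88.
- Paired t: n = 89.15; power at n = 89 is 79.9%.

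The stated 89 is reproduced to within rounding. No acuity quantity and no visit other than month 12 enters it, so the visit list in 9.3 does not affect it.

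**The visit lists side by side.**

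| Item | Source | Months |
|---|---|---|
| Acuity endpoint | 9.3, first sentence | 12 |
| Visits in the repeated-measures ANOVA | 9.3, last sentence | 1, 3, 6 |
| BSCVA measured after treatment | 8.3 | 1, 3, 6, 12 |
| UCVA measured after treatment | 8.3 | 1, 3, 6, 12 (also day 1 and week 1) |

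**What is left out, counting follow-up visits.**

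- BSCVA visits scheduled: 4. In the model: 3. Missing: 4 − 3 = 1, which is month 12.
- Successive-visit contrasts available from months 1, 3, 6 and 12: 1 to 3, 3 to 6 and 6 to 12, so 3. Available from the model as written: 1 to 3 and 3 to 6, so 2. Missing: 3 − 2 = 1, which is month 6 to month 12.
- UCVA at day 1 and week 1 is also outside the model, but BSCVA is not measured then and the endpoint is not at those visits, so no conflict arises.

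**Does another section supply month 12?** Section 9.2 concerns Kmax. Section 9.5 gives percentages at each time point, not a model of mean acuity. No section adds month 12 to the repeated-measures analysis or gives a reason for leaving it out.

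**Precision.** The protocol states no standard deviation for BSCVA or UCVA and no correlation between visits. A standard error or interval width for the month 6 to 12 contrast therefore cannot be derived from it.

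**The case against.** The strongest reply is that 9.3 divides the work: its first two sentences deal with month 12 descriptively, and the ANOVA is meant only to add the earlier course. On that reading nothing is lost at month 12, and the analysis is in any case one of the additional analyses, with no success criterion attached. The part about low stakes stands, and it is why the point is minor. The rest does not remove the problem. The sentence presents the model as an analysis of the 12-month endpoint and as a profile across time, and it is neither if it stops at month 6.

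A second reply is that late acuity loss is reported elsewhere. Section 9.5 asks, for each time point, for the share of eyes losing two or more BSCVA lines, so months 6 and 12 are both covered. This is correct and limits the harm. It does not give a mean change between the two visits, and it does not cover UCVA.

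A third reply concerns timing. Section 1.2 reports from the earlier trials that "decreased visual acuity took up to 6 months to resolve", which might be taken to justify a profile ending at month 6, or equally to show that the step after month 6 is the important one. Neither inference is safe. Those trials removed the epithelium, and section 1.1 lists faster visual recovery as a potential benefit of keeping it. The case for adding month 12 rests on the mismatch within 9.3, not on that history.

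A final reply is that the analysis plan may list the visits correctly. It may, but it would then depart from the protocol text, which would still need correcting.

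**Conclusion.** The point holds as a minor one. The visit list in 9.3 omits the endpoint visit of the analysis it describes: 1 of 4 scheduled BSCVA follow-up visits and 1 of 3 successive-visit contrasts. The conclusion assumes only that the endpoint referred to in the last sentence of 9.3 is the 12-month acuity change set out at its start, which is the only endpoint that section names.

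Three stronger readings are tempting and not supported.

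- A reader might infer that 12-month acuity goes unanalysed, or that the primary result is at risk. Section 9.3 keeps the descriptive month-12 summary, and 9.1, 9.2 and 9.5 do not depend on this model.
- A reader might infer that the reference in 4.0 to Kmax change over time makes the primary endpoint ambiguous in the same way. Sections 9.1 and 9.2 make it specific as the change at 12 months.
- A reader might infer that adding month 12 would limit the analysis to 89 eyes. Section 6.0 gives 89 of about 100 as the minimum evaluable number at month 12, not a ceiling. The number of eyes with a missing visit is not known in advance.

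**What to change.** In 9.3, change the visit list to months 1, 3, 6 and 12 for both BSCVA and UCVA, and state that the month 6 to month 12 contrast will be reported with its 95% CI.

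Two conditions should go with this change. First, a conventional repeated-measures ANOVA drops any eye with a missing visit, which sits badly with the 9.1 rule that the ITT population serves all efficacy evaluations. The model should therefore retain eyes with some missing visits; a likelihood-based repeated-measures model is one example. Second, because 8.3 lets both eyes of a subject take part, the analysis should allow for correlation between two eyes of one subject.

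Relabelling the model as a description of the early course would also remove the contradiction, but it would leave the month 6 to 12 step without an estimate although the data are collected.

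The cost is a short wording change and slight extra programming. No visit or measurement is added, and the primary analysis and sample size stay as they are. The downside is that a likelihood-based model assumes data are missing at random, which should be stated.
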